20.0 Data and Safety Monitoring Plan

20.1 Describe the plan for monitoring data and safety (Help Text updated 9/13):

One of the study investigators will be present during the study acquisition and will document any possible adverse reaction on a log book. [name] and [name] will review the log book to confirm absence of adverse events once a week. In case of a minor adverse event, CHR will be informed within one week. In the unlikely event of a significant adverse event, CHR will be informed within 24 hours.

20.2 This study requires a Data and Safety Monitoring Board:

Yes
 No or not sure

If **yes**, press **SAVE and CONTINUE** to move to the next section of the application.

20.3 If No, provide rationale:

- Social/Behavioral research
- Phase I trial
- Treatment IND/Compassionate Use Trial
- Other (explain below)

If **Other**, explain:

It does not make criteria for the Data and Safety Monitoring Board.

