13.0 Study Drug Details**13.1 List the drugs or biologics that will be studied:**

View Details	Drug Name	FDA Approved	A new drug or a new use of approved drug:	IND Number
	Trade Drug Name: Gadavist Generic Drug Name: Gadobutrol Investigational Drug Name:	Yes	No	
Trade Drug Name:		Gadavist		
Generic Drug Name:		Gadobutrol		

Investigational Drug Name:	
Identify the name of the manufacturer or source of investigational drug/biologic:	
Is the drug supplied at no cost?	No
Is the Drug FDA Approved:	Yes
Is this a new drug or a new use of an already approved drug	No
Is an IND necessary	No
IND Number	
Who holds the IND:	N/A
IND details:	
If FDA Approved and an IND is not required, Please provide a rationale for exemption:	This drug is currently used in MRI exams.
Are you currently using this IND in another research project?	No
If yes, list the IRB Number(s):	
Will the investigational pharmacy be dispensing?	No
If the source is not a FDA licensed facility, provide details regarding the purity, quality, stability and sterility of the investigational drug /biologic:	

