17.0 Procedures

17.1 * Procedures/Methods [Help Text updated 9/13] For clinical research list all study procedures, test and treatments required for this study, including when and how often they will be performed. If there are no clinical procedures, describe the Methods:

The subjects will undergo PET/MR for study purposes after they have finished their clinically indicated PET/CT, with no additional venipuncture to the patients.

We propose to use 5D MR imaging (3D in space, in time through the cardiac cycle, and in time through the respiratory cycle) to provide improved information on the location of the signal source during PET acquisition.

Dynamic and static PET data will be acquired in list mode and retrospectively rebinned according to predicted location from MR data.

Accelerated MR methods (including compressed sensing) will be used to give rapid assessment of volumes over time.

Additional MR imaging sequences will include strain mapping and VEC-MRI for flow imaging. In addition gadolinium delayed enhancement will be obtained for myocardial tissue characterization with MRI.

If you have a procedure table, attach it to the submission with your other study documents.

17.2 Interviews, questionnaires, and/or surveys will be administered or focus groups will be conducted:

Yes No

List any standard instruments used for this study:

Attach any non-standard instruments at the end of the application.

17.3 Conduct of study procedures or tests off-site by non-UCSF personnel:

Yes No

If yes, explain:

17.4 Sharing of experimental research test results with subjects or their care providers:

Yes No

If yes, explain:

17.5 * Specimen collection for future research and/or specimen repository/bank administration:

Yes No

17.6 Time commitment (per visit and in total):

1 hour in the scanner.

17.7 Locations:

The cardiac MRI will take place at the China Basin radiology.

17.8 Describe the resources in place to conduct this study in a way that assures protection of the rights and welfare of participants:

1. The research team will make several efforts to keep the PHI under extreme security, including the use of a coded database, password protected computers and locked cabinets, which will all be kept inside a locked office at the Parnassus campus.
2. Patients are screened for prior claustrophobic symptoms using a screening form. Earplugs are provided to all patients in order to minimize the discomfort related to the loud noise.

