19.0 Risks and Benefits

19.1 * Risks and discomforts:

The main risks to subjects for participating in this study are related to breach of confidentiality and exposure to the MRI scanner.

No significant physical, psychological, financial, or legal harm is anticipated in case subject's confidentiality is inadvertently breached.

Risks associated with the MRI study are stratified based on probability of occurrence and listed below:

Common:

MR imaging may cause some discomfort, such as feelings of claustrophobia and discomfort due to loud sounds of the MR instrument during the study.

Uncommon/Rare:

Another potential hazard of the exam is localized heating of the body due to the radio waves employed. MR scanner and the MR probes have been designed to reduce the chance of heating.

Because the MR scanner attracts iron, there is a small possibility that an iron-containing object could accidentally fly into the magnet causing injury to the patient.

The presence of some metallic implantable devices or foreign bodies represents formal contra-indication to MR imaging and exposure to the strong magnetic field may cause malfunction or dislodgement of such devices or foreign bodies, potentially harming patients. A cardiac pacemaker is one example.

Gadolinium is considered to be very safe for most people. Side effects from gadolinium itself are very rare. These side effects are usually headache and nausea. There have been a very few people who have had allergic reactions to gadolinium. Most people with allergic reactions get hives. Patients with severe kidney disease sometimes have a bad reaction to gadolinium contrast. The condition is called nephrogenic systemic fibrosis (NSF). It can cause skin to tighten or scar and can damage internal organs. Sometimes it can be life threatening. There are no reports of NSF in patients with normal kidney function.

19.2 Steps taken to minimize risks to subjects:

- 1) The research team will make several efforts to keep the PHI under extreme security, including the use of a coded database, password protected computers and locked cabinets, which will all be kept inside a locked office at the Parnassus campus.
- 2) Patients are screened for prior claustrophobic symptoms using a screening form. Earplugs are provided to all patients in order to minimize the discomfort related to the loud noise.

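### Section 20.1 states no route for finding reactions to the study contrast agent that start after the scan

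*Combined protocol and SAP*

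**What the plan says.** Section 20.1 (Data and Safety Monitoring Plan) describes how adverse events are found: "One of the study investigators will be present during the study acquisition and will document any possible adverse reaction on a log book". Two named members of the team "will review the log book to confirm absence of adverse events once a week". Two reporting times to the ethics committee (CHR) follow: "In case of a minor adverse event, CHR will be informed within one week", and "In the unlikely event of a significant adverse event, CHR will be informed within 24 hours".

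Section 17.6 gives the subject's time commitment, per visit and in total, as "1 hour in the scanner". Section 17.1 makes contrast part of the study scan: "In addition gadolinium delayed enhancement will be obtained for myocardial tissue characterization with MRI". Section 13.1 lists the agent: "Trade Drug Name: Gadavist Generic Drug Name: Gadobutrol". Under section 18.2, a patient who declines receives only the clinical FDG PET-CT, so the contrast exposure comes from taking part.

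Section 19.1 lists headache, nausea and hives as gadolinium effects. It also lists NSF, which it links to severe kidney disease and describes so: "It can cause skin to tighten or scar and can damage internal organs". Section 19.2 adds needle-site discomfort, bruising and, rarely, infection. It also describes the renal-function check before contrast, and section 11.7 excludes subjects on eGFR. Section 24.6 says that all data will be destroyed once the study is finished.

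**The concern.** The listed harms and the observation window do not match. Sections 19.1 and 19.2 name events that could plausibly appear hours, days or longer after the visit. Section 20.1 plans observation only while the subject is being scanned, and the weekly review adds no new source of information. For anything that starts later, an empty log is what the plan would produce at almost any true rate, apart from events that a patient or clinician happens to report.

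Two things are at stake. A delayed reaction to an agent given for research could go unnoticed by the team, so neither reporting time in section 20.1 would start. And a weekly entry that no adverse events occurred could be read as covering more than was observed.

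**Working it through.** The documents give no adverse-event rate, safety sample size or safety analysis, so there is no plan figure to reproduce. The main check is a comparison of sections. The arithmetic after it is illustrative.

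**Step 1: harms against capture routes**

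| Harm named in 19.1 or 19.2 | Could it start after the scan? | Stated route to find it then |
|---|---|---|
| Headache, nausea | Possibly; no timing given | None |
| Hives | Possibly; no timing given | None |
| Needle-site bruising | Possibly; no timing given | None |
| Needle-site infection | Expected later | None |
| NSF (skin tightening or scarring, organ damage) | Expected later | None |

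The documents give no onset times. The middle column is inferred from the nature of each event, and is firm only for infection and NSF.

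**Step 2: other places where a route could sit**

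- Section 17 (procedures): no post-scan contact.
- Section 19.2 (risk minimisation): renal-function check before contrast. This is prevention and records no events.
- Section 20.1 (monitoring): the two reporting times apply once an event is known. They do not create a way of learning of one.
- Sections 23.2, 23.3 and 24.5 (recruitment): telephone contact and screening for contraindications, both before the scan.

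**Step 3: what an empty log would show (illustration)**

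Inputs: n = 60 (section 11.1) and n = 50 (section 11.4), assuming every subject is dosed and observed. With no events in n subjects, the exact one-sided 95% upper bound on the event rate is 1 − 0.05^(1/n).

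- n = 60: 1 − 0.05^(1/60) = 1 − exp(−2.9957/60) = 0.0487, or 4.9%.
- n = 50: 1 − 0.05^(1/50) = 1 − exp(−2.9957/50) = 0.0582, or 5.8%.

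These bounds apply only to events within the observed period. For later events the number of subjects under planned observation is zero, so there is no bound.

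**Step 4: what follow-up could add (assumed rates)**

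The chance of seeing at least one late event under complete follow-up is 1 − (1 − p)^n, where p is an assumed rate.

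| Assumed late-event rate p | n = 50 | n = 60 |
|---|---|---|
| 0.5% | 22% | 26% |
| 1% | 40% | 45% |
| 2% | 64% | 70% |
| 5% | 92% | 95% |

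If follow-up found only half of such events, the 2% row at n = 60 would become 1 − (1 − 0.01)^60 = 45%. With no planned follow-up, the chance is zero apart from unprompted reports.

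**The case against.** The strongest reply is that section 20.1 is silent on later events and does not exclude them. It gives the log no closing time, and an unprompted report could be entered. Inpatients are among those invited (section 23.1), so some subjects stay under clinical care, and the consent pages, which might carry contact instructions, are not available here. All of this stands. A reader might infer that later events cannot be recorded. The documents support only that there is no stated route to find them.

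Other parts of the reply also stand:

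- **NSF.** Section 19.1 ties it to severe kidney disease and notes no reports with normal kidney function. The eGFR exclusion, the pre-contrast renal check and a doctor's decision all lower the risk. None of them records an event.
- **Needle-site harms.** Section 17.1 says the study adds no venipuncture, so bruising or infection may belong partly or wholly to the clinical PET/CT.
- **Time observed after injection.** A reader might conclude that it is only minutes, from the 5–20 minute imaging delay in section 10.2. That is literature background on a different agent (Gd-DTPA). Section 17.1 gives neither the injection time nor the order of sequences.
- **Use of the safety result.** Section 11.4 says that the pilot informs a sample-size calculation. No aim in section 9.2 and no analysis in section 9.3 concerns safety, so the documents do not support saying that an unfounded safety claim passes to the larger trial.
- **Reporting times.** Weekly review beside a 24-hour notice might suggest an overrun of up to 6 days (7 minus 1). But the 24-hour sentence does not depend on the weekly review, and the person in the room is an investigator who could report at once. The overrun is hypothetical.

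The reply does not supply a capture route for reactions that start after the scan. It makes the point narrower without removing it.

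**Conclusion.** The point holds as a gap in adverse-event capture. Followed as written, section 20.1 looks for reactions only during the acquisition, and its weekly review cannot add to that. At least NSF and infection, both named in the protocol, would be expected to fall outside this window. Hives, headache and nausea might.

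The size cannot be given as a rate. The 4.9% and 5.8% bounds are illustrations for in-session events, not quantities that the study plans to report. What can be said is that no subject has planned observation for later events.

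The conclusion rests on two assumptions: that onset can be inferred from the nature of the harms, and that the unavailable consent pages do not already set up systematic follow-up. Contact instructions alone would leave detection to the patient. Given the renal screening and the absence of any safety aim, this is a worthwhile, low-cost improvement. It does not affect the imaging comparisons.

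**What to change.** In section 20.1, for every subject given gadobutrol:

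1. Add one short telephone contact after the scan and one medical-record check before study close, and before the data destruction in section 24.6. State the time of each. The investigators should choose times suited to the harms they list, since the documents give no onset times and one early call could not be relied on to detect NSF.
2. Enter both in the existing log and have the weekly review cover them.
3. Limit any statement that no adverse events occurred to the period observed and the number of subjects actually followed, with in-scan and post-scan events reported separately.
4. As a clarification only, state that the investigator present reports a significant event without waiting for the weekly review.

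The cost is a protocol amendment and, for at most 60 subjects, one call and one chart look-up each. The investigators already telephone these patients and screen for contraindications at recruitment (sections 23.2, 23.3 and 24.5), so no new staff, procedure or subjects are needed. The downside is minor staff time and a few incidental events to classify, some of which may belong to the clinical PET/CT.

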21.0 Confidentiality and Privacy

21.1 Plans for maintaining privacy in the research setting:

The research team will make several efforts to keep the PHI under extreme security, including the use of a coded database, password protected computers and locked cabinets, which will all be kept inside a locked office at the Parnassus campus.

21.2 Possible consequences to subjects resulting from a loss of privacy:

No significant physical, psychological, financial, or legal harm is anticipated in case subject's confidentiality is inadvertently breached.

21.3 Study data are:

- Derived from the Integrated Data Repository (IDR) or The Health Record Data Service (THREDS) at SFGH
- Derived from a medical record (e.g. APeX, OnCore, etc. Identify source below)
- Added to the hospital or clinical medical record
- Created or collected as part of health care
- Used to make health care decisions
- Obtained from the subject, including interviews, questionnaires
- Obtained from a foreign country or countries only
- Obtained from records open to the public
- Obtained from existing research records
- None of the above

~~If derived from a medical record, identify source:~~

21.4 Identifiers may be included in research records:

Yes No

If **yes**, check all the identifiers that may be included:

- Names
- Dates
- Postal addresses
- Phone numbers
- Fax numbers
- Email addresses
- Social Security Numbers*
- Medical record numbers
- Health plan numbers
- Account numbers
- License or certificate numbers
- Vehicle ID numbers
- Device identifiers or serial numbers
- Web URLs
- IP address numbers

- Biometric identifiers
- Facial photos or other identifiable images
- Any other unique identifier

* Required for studies conducted at the VAMC

21.5 Identifiable information might be disclosed as part of study activities:

Yes No

If **yes**, indicate to whom identifiable information may be disclosed:

- The subject's medical record
- The study sponsor
- Collaborators
- The US Food & Drug Administration (FDA)
- Others (specify below)
- A Foreign Country or Countries (specify below)

If **Others**, specify:

21.6 Indicate how data are kept secure and protected from improper use and disclosure (check all that apply): NOTE: Whenever possible, do not store subject identifiers on laptops, PDAs, or other portable devices. If you collect subject identifiers on portable devices, you MUST encrypt the devices.

- Data are stored securely in My Research
- Data are coded; data key is destroyed at end of study
- Data are coded; data key is kept separately and securely
- Data are kept in a locked file cabinet
- Data are kept in a locked office or suite
- Electronic data are protected with a password
- Data are stored on a secure network
- Data are collected/stored using REDCap or REDCap Survey
- Data are securely stored in OnCore

21.7 Additional measures to assure confidentiality and protect identifiers from improper use and disclosure, if any:

Yes No

Explain:

21.9 This study will be issued a Certificate of Confidentiality:

Yes No

22.0 Subjects

22.1 Check all types of subjects that may be enrolled:

- Inpatients
- Outpatients
- Healthy volunteers
- Staff of UCSF or affiliated institutions

22.2 Additional vulnerable populations:

- Children
- Subjects unable to consent for themselves
- Subjects unable to consent for themselves (emergency setting)
- Subjects with diminished capacity to consent
- Subjects unable to read, speak or understand English
- Pregnant women
- Fetuses
- Neonates
- Prisoners
- Economically or educationally disadvantaged persons
- Investigators' staff
- Students

Explain why it is appropriate to include the types of subjects checked above in this particular study:

Describe the additional safeguards that have been included in the study to protect the rights and welfare of these subjects and minimize coercion or undue influence:

23.0 Recruitment

23.1 * Methods (check all that apply):

- Study investigators (and/or affiliated nurses or staff) recruit their own patients directly in person or by phone.
- Study investigators recruit their own patients by letter. Attach the letter for review.
- Study investigators send a "Dear Doctor" letter to colleagues asking for referrals of eligible patients. If interested, the patient will contact the PI or the PI may directly recruit the patients (with documented permission from the patient). Investigators may give the referring physicians a study information sheet for the patients.
- Study investigators provide their colleagues with a "Dear Patient" letter describing the study. This letter can be signed by the treating physicians and would inform the patients how to contact the study investigators. The study investigators may not have access to patient names and addresses for mailing
- Advertisements, notices, and/or media used to recruit subjects. Interested subjects initiate contact with study investigators. Attach ads, notices, or media text for review. In section below, please explain where ads will be posted.
- Study investigators identify prospective subjects through chart review. (Study investigators request a Waiver of Authorization for recruitment purposes.)
- Large-scale epidemiological studies and/or population-based studies: Prospective subjects are identified through a registry or medical records and contacted by someone other than their personal physician. (Study investigators request a Waiver of Authorization for recruitment purposes.)
- Direct contact of potential subjects who have previously given consent to be contacted for participation in research. Clinic or program develops a CHR-approved recruitment protocol that asks patients if they agree to be contacted for research (a recruitment database) or consent for future contact was documented using the consent form for another CHR-approved study.
- Study investigators list the study on the School of Medicine list of UCSF Clinical Trials website or a similarly managed site. Interested subjects initiate contact with investigators.

Study investigators recruit potential subjects who are unknown to them through methods such as snowball sampling, direct approach, use of social networks, and random digit dialing.

Other

If **Other**, explain:

Inpatients and outpatients referred for clinically indicated FGD-PET are going to be invited for participation in this study. The investigators will explain in detail the study and will provide the informed consent to the potential subject. The investigators will clarify any doubts related to the informed consent and/or the study.

23.2 * How, when, and by whom eligibility will be determined:

The patients will be approached (by phone call) by one of the investigators before they arrive at the Radiology department for the clinically indicated FGD-PET.

23.3 * How, when, where and by whom potential subjects will be approached:

The investigator will look for exclusion criteria of scheduled patients for FGD-PET . The patients will be approached by phone call before their scheduled appointment at the Radiology department for the clinically indicated FGD-PET.

23.4 * Protected health information (PHI) will be accessed prior to obtaining consent:

Yes No

24.0 Waiver of Consent/Authorization for Recruitment Purposes

This section is required when study investigators (and/or affiliated nurses or staff) recruit their own patients directly.

24.1 * Study personnel need to access protected health information (PHI) during the recruitment process and it is not practicable to obtain informed consent until potential subjects have been identified:

Yes

If **no**, a waiver of consent/authorization is NOT needed.

24.2 * A waiver for screening of health records to identify potential subjects poses no more than minimal risk to privacy for participants:

Yes

If **no**, a waiver of authorization can NOT be granted.

24.3 * Screening health records prior to obtaining consent will not adversely affect subjects' rights and welfare:

Yes

If **no**, a waiver of authorization can NOT be granted.

24.4 * Check all the identifiers that will be collected prior to obtaining informed consent:

- Names
- Dates
- Postal addresses
- Phone numbers
- Fax numbers
- Email addresses
- Social Security Numbers*
- Medical record numbers
- Health plan numbers
- Account numbers
- License or certificate numbers
- Vehicle ID numbers
- Device identifiers or serial numbers
- Web URLs
- IP address numbers
- Biometric identifiers
- Facial photos or other identifiable images
- Any other unique identifier
- None

Note: HIPAA rules require that you collect the minimum necessary.

24.5 * Describe any health information that will be collected prior to obtaining informed consent:

Name, phone number and presence of contraindications (history of cardiac pacemaker, retained metallic foreign body, cochlear implant, aneurysm clip in the brain, claustrophobia, pregnancy and eGFR less than 45%) to the MR exam.

Note: HIPAA requires that you collect the minimum necessary.

24.6 * Describe your plan to destroy the identifiers at the earliest opportunity consistent with the research or provide a health or research justification for retaining the identifiers, or indicate and explain that retention is required by law:

As soon as this study is finished, all the data will be destroyed, physically and virtually.

